14.3.1 Summary of Adverse Events

A summary table of all AEs will be prepared, summarizing the number and percentage of patients with at least 1 AE and the total number of AEs in the following categories:

1. AEs that occurred during screening
2. TEAEs
3. TEAEs occurring within 12 hours after dosing
4. TEAEs, which are AESIs
5. TEAEs, which are an other important event
6. TEAEs, which are injection site reactions based on investigator assessment on the eCRF
7. IMP related TEAEs
8. TEAEs, which are SAEs
9. IMP related TEAEs, which are SAEs
10. Deaths

14.3.2 Adverse Events by SOC and PT Terms

The analysis of AEs will include summary tables displaying the counts and percentages of patients experiencing AEs by SOC and PT. If a patient has more than 1 AE which codes to the same PT, the patient will be counted only once for that PT. The total number of events documented per SOC and PT will also be displayed. Summaries will be ordered by descending order of incidence of SOC and PT, within each SOC based on the frequency (proportion of patients) in the dasiglucagon group.

Frequency tables will be prepared by MedDRA terms (SOC and PT) summarizing the categories 1 to 9 as listed in Section 14.3.1.

All details relating to adverse events will also be provided in a data listing. Additional listings will be produced to display: AEs for screening failures, any AESIs, AEs leading to discontinuation of IMP, SAEs and any AEs leading to death.

14.4 Clinical Laboratory Evaluation

Laboratory parameters (clinical chemistry, hematology, coagulation) for continuous results will be summarized using descriptive statistics at baseline and at each post-baseline time point. Changes from baseline will also be summarized.

The numbers in each category (above/below/within the relevant reference ranges) will be counted and percentages presented for each laboratory test result at each scheduled visit.

Three separate listings will be produced, which will include all data related to clinical chemistry, hematology, and coagulation laboratory tests.

14.5 Vital Signs

Vital signs will be summarized using descriptive statistics at baseline and at each scheduled post-baseline visit and time point. Changes from baseline will also be summarized.

Categorical results for interpretation (normal/abnormal) will be summarized using frequency counts at baseline and at each scheduled post-baseline visit and time point.

All data related to vital signs will also be included in a data listing.

14.6 Physical Examination

Physical examination results will be included in data listings only.

14.7 Electrocardiogram

The following 12-lead ECG parameters will be summarized using descriptive statistics at screening.

- Heart Rate (beats/min)
- PR Interval (msec)
- QRS Interval (msec)
- QT Interval (msec)
- QTc Interval (msec)
- QTcF Interval (msec) [QTc calculated using Fredericia's formula]

Additionally, the number of patients with an ECG interpretation of normal/abnormal clinically significant/abnormal not clinically significant will be summarized at screening.

All ECG data will also be provided in a data listing.

14.8 Food and Drink Intake

Data collected on the food and drink intake of patients at Visit 2 (pre-dose and post-dose) will be provided in a data listing only.

14.9 Continuous Glucose Monitoring

CGM data will be presented graphically as individual plots (per patient) of glucose measurements over time, from the time of stopping the participant's insulin pump to 300 minutes after dasiglucagon administration.

A secondary y-axis will be displayed to show Glucose measurements in mmol/L additionally to mg/dl. Results are converted into the unit 'mmol/L' by using the conversion factor 0.0555 (i.e. Glucose [mmol/L]=Glucose [mg/dl] *0.0555).

All CGM data will also be included in a data listing.

14.10 Glucose Analyzer Data

Glucose Analyzer data will be summarized by time point and included in a data listing.

In addition, individual time-concentration curves will be created using the time of first dosing of IMP as relative starting point.

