6.5.1 Hypoglycemic Clamp Procedure and Dosing

Hypoglycemia induction will be initiated using IV insulin to target a plasma glucose level between 70 and 90 mg/dL (between 3.9 and 5 mmol/L).

Version 6.0, 12 Jul 2024

Insulin (only insulin glulisine [Apidra®] will be used) will be provided by the investigator. Insulin infusion for IV use will be prepared according to the patient's body weight at the dosing visit.

Preparation of the insulin infusion:

- 0.5 international units insulin glulisine (Apidra®) per kg body weight
- 48 mL NaCl 0.9%

Zealand Pharma A/S

Plasma glucose must be checked using glucose analyzer before initiation of induction of hypoglycemia. Hypoglycemia will be induced using insulin IV infusion rates according to plasma glucose levels according to Table 6-2.

Table 6-2 Insulin Infusion Rates

Glucose	Infusion rate	Insulin dose (IU/kg BW/h)
>200 mg/dL	10.0 mL/h	0.1
150-200 mg/dL	5.0 mL/h	0.05
90–149 mg/dL	2.5 mL/h	0.025
<90 mg/dL	Insulin infusion stop!	0

Abbreviations: BW=body weight; IU=International units

The procedure to induce hypoglycemia is given as a guidance and any deviation to increase or decrease the insulin rate is allowed at the discretion of the investigator. If the target plasma glucose cannot be achieved on the dosing day, the patient can be rescheduled for another visit as described in Section 5.5.

During the induction phase (during insulin infusion) and following the administration of dasiglucagon, glucose levels will be monitored by both CGM and by a glucose analyzer (see Section 6.1.1). Plasma glucose levels should preferably be checked by glucose analyzer approximately every 10 minutes while glucose levels are above 110 mg/dL (6.1 mmol/L), and preferably approximately every 5 minutes once glucose levels are at or below 110 mg/dL (6.1 mmol/L). Plasma glucose should be confirmed by the glucose analyzer prior to the administration of dasiglucagon. After dosing with dasiglucagon, once glucose levels reach ≥110 mg/dL (6.1 mg/dL), glucose levels should preferably be checked approximately every 30 minutes until 300 minutes. The monitoring frequency of plasma glucose via the glucose analyzer should be adjusted as needed based on the child's body weight to ensure that a maximum of approximately 1.5% is obtained during the dosing visit as specified in Section 6.5.3 (1.5% equals 1.13 to 1.20 mL/kg with the total blood volume estimated to be 75 to 80 mL/kg).⁵

[figure not shown]

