At the discretion of the investigator, additional plasma glucose measurements can be taken at any time during the trial, for example when there is a suspicion (eg, symptoms) of a hypoglycemic episode.

A catheter (eg, an indwelling catheter) will be inserted into the child's arm for blood draw for PK/PD sampling. If possible, the same IV access as used for insulin infusion can be used for the PK/PD sampling to reduce the stress and discomfort for the child. Attention should be made to ensure blood samples will be collected from the circulating blood volume and not from a reservoir dead space created by the catheter. If direct venipunctures are considered more appropriate, especially for those children where the number of PK and PD samples are reduced (refer to Table 6-4), venipunctures can be used instead of indwelling catheters. The catheter will be placed in the morning prior to IMP administration. Blood samples for baseline assessment of plasma glucose and dasiglucagon PK will be collected approximately 5 minutes after the glucose concentration reaches >70 mg/dL and < 90 mg/dL (3.9 to 5.0 mmol/L). These samples are the baseline samples and should be collected within 2 minutes before IMP administration. The baseline samples will be sent to the clinical laboratory and analyzed using a sensitive and validated assay for glucose measurements. The assay used for primary endpoint glucose measurements should fulfil the requirements of the US FDA Bioanalytical Method Validation Guidance for Industry Section 5 B and C for biomarkers. ⁶ The sampling procedure is described in Section 6.5.3. Before IMP administration, it must be confirmed by the glucose analyzer that the plasma glucose is still ≥70 mg/dL and <90 mg/dL.

If plasma glucose is < 70 mg/dL (3.9 mmol/L), IV glucose solution will be administered to raise plasma glucose to within the 70 to 90 mg/dL (3.9 to 5.0 mmol/L) target range. The run-in period will be adequately extended (at least 30 minutes) until the above target is achieved, the glucose infusion has been discontinued, and new baseline samples for plasma glucose will be collected. In this case, glucose should not be infused within 30 minutes before IMP administration. If plasma glucose is not within the target range after the second attempt, the patient should be rescheduled for a new treatment visit within 7 days (+2 days).

Insulin-Induced Hypoglycemia and Dosing Figure 6-1

Abbreviations: IV=intravenous; PG=plasma glucose

Zealand Pharma A/S

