- Plasma glucose using glucose analyzer during induction of hypoglycemia and until 300 minutes after dosing. Plasma glucose levels must be checked by glucose analyzer approximately every 10 minutes while glucose levels are above 110 mg/dL (6.1 mmol/L), and approximately every 5 minutes once glucose levels are at or below 110 mg/dL (6.1 mmol/L). Plasma glucose should be confirmed by the glucose analyzer prior to the pre-dose PK and PD samples and prior to the administration of dasiglucagon. After dosing with dasiglucagon, once glucose levels reach ≥110 mg/dL (6.1 mg/dL), glucose levels should be checked approximately every 30 minutes until 300 minutes.
- Glucose levels using CGM during induction of hypoglycemia and until 300 minutes after dosing. Dexcom 6 will be fitted in the morning at Visit 2 and must remain fitted until 300 minutes after IMP administration.
- Administration of IMP (during hypoglycemic clamp procedure)

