5. DETERMINATION OF SAMPLE SIZE

Eight children will be treated in this trial. The number of children is not based on a formal sample size calculation, evaluating the power of the trial, however some considerations have been made with respect to the precision of the estimate of the primary endpoint. In a previous pediatric trial with dasiglucagon (Trial ZP4207-17086), the mean plasma glucose change from baseline at 30 minutes after IMP injection was 96 mg/dL with a standard deviation (SD) of 20 mg/dL in children aged 6 to 11 years. Assuming the variation is the same in children < 6 years

of age, a 95% confidence interval will have a width of ± 25 mg/dL around the mean plasma glucose change with 95% probability, when 8 children are treated.

The power procedure in SAS with the onesamplemeans statement have been applied for the sample size consideration.

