6. GENERAL ANALYSIS CONSIDERATIONS

The statistical analyses will be reported using TLFs. The International Council for Harmonisation of Technical Requirements for Pharmaceuticals for Human Use (ICH) numbering convention will be used for all TLFs.

Continuous variables will be summarized by presenting the number of observations, means, SDs, medians, minimums, and maximums. In addition, 95% confidence intervals (based on a *t* distribution if not otherwise stated) will be calculated if appropriate and detailed in the table shells. For logarithm-transformed data (relevant for selected PK summaries), the geometric mean and coefficient of variation % will also be provided.

Categorical variables will be summarized by presenting counts and percentages of subjects in corresponding categories. All possible categories as defined in the CRF should be populated, even if they have zero counts. Percentages for missing values are omitted and do not account for the percent calculation of other categories. Percentages are based on the total category count excluding the missing category if not otherwise mentioned. In certain tables (eg, AEs), the total number of subjects is used as the denominator. Footnotes will specify the percent basis in those cases.

All data collected in this trial and documented in the eCRFs will be presented in data listings. In case of termination of the trial, all data collected up to that time point will be included in the analysis.

All summary tables will be presented for the two treatment groups and total.

Individual subject data obtained from the eCRFs, external vendors, central clinical laboratory, central ECG laboratory, PK data, and any derived data will be presented by subject in data listings.

The analyses described in this plan are considered a priori, in that they have been defined before first patient dosed in the study. Any analyses performed after first patient dosed will be considered post hoc and exploratory. Post hoc analyses will be labeled as such on the output and identified in the CSR.

All analyses and tabulations will be performed using SAS® statistical software, version 9.4 or higher (SAS Institute Inc., Cary, North Carolina, USA). PK and PD analyses will be performed using Phoenix® WinNonlin®, version 8.3.4 or higher (Certara USA, Inc., Princeton, New Jersey, USA). This software was validated by Syneos Health in compliance with US 21 CFR Part 11 Regulation.

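### By-time-point means of the glucose-analyzer data at about 20–30 minutes would come mainly from slower responders, because the post-dose checking interval depends on the glucose value

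*SAP*

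**What the plan says.** SAP 14.10, within the safety analyses: "Glucose Analyzer data will be summarized by time point and included in a data listing". It adds individual curves timed from dosing. SAP 6 gives the statistics: "Continuous variables will be summarized by presenting the number of observations, means, SDs, medians, minimums, and maximums", by dose group and in total. SAP 10.4 allows no imputation and uses observed data only.

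The protocol sets the analyzer interval by the current value:

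- At or below 110 mg/dL, section 6.5.1 asks for checks "preferably approximately every 5 minutes once glucose levels are at or below 110 mg/dL".
- After dosing, once a child is at or above 110 mg/dL, "glucose levels should preferably be checked approximately every 30 minutes until 300 minutes". Section 8.1.2 repeats the rule in firmer words: "glucose levels should be checked approximately every 30 minutes until 300 minutes".
- Section 6.5.1 also adjusts the frequency to body weight and allows extra readings at the investigator's discretion.

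No nominal post-dose analyzer times are given. Appendix B lists a Glucose Analyzer Data entry as 14.3.6.2, without the Figure tag, and uses the same number again for laboratory data. In Appendix C, 14.3.6.2 is a figure of individual analyzer profiles, and no by-time analyzer table has a shell. Listing 16.2.5.9 holds collection date and time but no planned time point.

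**The concern.** A by-time mean describes the group only if having a reading at that time is unrelated to the glucose level. Here it is related by design. A child who reaches 110 mg/dL at 10 minutes is next due at about 40 minutes, while a child who has not responded is read at 15, 20, 25, 30 and 35 minutes. With observed data only, the mean at an intermediate time averages the children still at or below 110 mg/dL and those just crossing it.

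The analyzer is the only plasma glucose series after 30 minutes and between the laboratory samples, so a reader may take such a table as the group's glucose profile. Because no windows are defined, the programmer would also have to choose them with the data in hand, in an open-label trial.

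**Working it through.** **Inputs from the documents.** Protocol 6.5.1 sets glucose at dosing: "it must be confirmed by the glucose analyzer that the plasma glucose is still ≥70 mg/dL and <90 mg/dL". SAP 5 gives the expected response, from children aged 6 to 11: "the mean plasma glucose change from baseline at 30 minutes after IMP injection was 96 mg/dL with a standard deviation (SD) of 20 mg/dL". There are 8 children. The checking rule is as above.

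**The plan's own figure.** SAP 5 states that the 95% confidence interval has a half-width of at most 25 mg/dL with 95% probability when n = 8 and the SD is 20. The half-width is t(0.975, 7)·S/√8 with t = 2.365, so S must be at most 25·√8/2.365 = 29.9. Then P(χ² on 7 df ≤ 7·29.9²/20² = 15.65) = 0.97. For n = 7 the probability is 0.91. The statement reproduces, and I use the same 96 and 20 below.

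**Average child, straight-line rise (assumed).** The rate is 96/30 = 3.2 mg/dL per minute. Starting from 90, 110 is reached at 20/3.2 = 6.3 minutes. Starting from 70, it is reached at 40/3.2 = 12.5 minutes. On a 5-minute grid the first reading at or above 110 is at 10 or 15 minutes and the next at 40 or 45. This child has no analyzer reading from 20 to 35 minutes.

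**Simulation.** 200,000 children per scenario; baseline uniform on 70–90; checks every 5 minutes until the first reading at or above 110, then 30 minutes later. At each time the mean of children read is compared with the mean of all children. The rise shape is not in the documents and is assumed. Rescue glucose is not modelled. All rows except the first and last add reading error with SD 3.

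| Rise at 30 min (mean/SD), shape | Minute | Children read, of 8 | Mean, all | Mean, read | Difference |
|---|---|---|---|---|---|
| 96/20, straight line | 20 | 0.5 | 144 | 115 | −29 |
| | 25 | 0.1 | 160 | 113 | −47 |
| 96/20, 5-min lag | 20 | 2.0 | 137 | 121 | −16 |
| | 25 | 0.2 | 157 | 118 | −39 |
| 96/20, 8-min lag | 20 | 4.2 | 132 | 122 | −10 |
| | 25 | 0.5 | 154 | 124 | −30 |
| 96/20, convex (power 1.5) | 20 | 2.8 | 132 | 120 | −12 |
| | 25 | 0.3 | 153 | 119 | −34 |
| 96/35, 8-min lag | 25 | 1.2 | 154 | 113 | −41 |
| | 30 | 0.5 | 176 | 106 | −70 |
| 60/20, 5-min lag | 20 | 5.8 | 116 | 110 | −6 |
| | 30 | 1.2 | 140 | 108 | −32 |
| 60/40, straight line | 30 | 2.2 | 140 | 91 | −49 |

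With reading error, the straight-line differences are −27 and −46. At 20 minutes, 69–100% of readings come from the slower half of children. At 25 and 30 minutes it is 99–100%.

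**Edges of the window.**

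- 15 minutes: under 96/20 the difference is about −10 with a straight line but only about −1 to −2 with a lag or convex rise.
- 30 minutes: under 96/20 the difference is about −60, but only 0.02–0.04 of 8 children are read and the cell is empty in about 97% of trials.
- 35 minutes: with a straight line the few readings come from the fastest children and the difference is about +35. Under the other 96/20 shapes the cell is almost empty.
- 40 minutes: fast responders are read again and the difference is positive in most scenarios (+42 with the convex rise), though −30 under 60/20. Figures past 30 minutes also assume that the rise continues.

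**Looser scheduling.** If every child is also read at clock time 30 minutes, the 30-minute difference is 0. Those at 20 and 25 minutes are unchanged.

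**The case against.** The table is a descriptive safety output. The primary and secondary endpoints use separate laboratory samples at fixed times, and no hypothesis is tested. Appendix C already has only individual curves and a listing for the analyzer. SAP 6 prints n, so a thin cell would be visible. Section 6.5.1 words the intervals as preferences and allows extra readings, and a 30-minute interval could be read as clock times. Individual CGM curves to 300 minutes are also planned.

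Most of this stands, and it limits the point to one table. It does not remove it: SAP 14.10 and the index still call for the summary, nothing in the SAP recognises value-dependent sampling, and printing n does not tell the reader which children are missing. CGM measures interstitial rather than plasma glucose.

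A reader might infer more than the documents support:

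- *That all means from 15 to 35 minutes are too low.* The bias can be slight at 15 minutes and upward at 35.
- *That the table would contradict the 30-minute primary result.* Under the SAP's 96/20 and the value-driven schedule, the 30-minute analyzer cell is nearly always empty. The contrasts with more children need a weaker or more variable assumed response.
- *That a dose comparison would be distorted.* The plan makes no formal comparison and only shows the dose groups side by side.
- *That interpolating each child to fixed times is the cure.* It conflicts with SAP 10.4 and would often bridge the fastest part of the rise and the start of eating at 35 minutes.

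**Conclusion.** The concern holds in limited form. If sites follow the value-driven schedule, by-time analyzer means at about 20–30 minutes rest mainly on slower responders and understate the group mean. That direction held under every rise shape tried, except at 30 minutes when all children are also read at that clock time. The size is illustrative: about 10–29 mg/dL at 20 minutes and 30–47 at 25 under 96/20, often from fewer than one child in 8. It rests on an assumed time course and on an SD from children aged 6 to 11. Outside that window the bias may be negligible or reversed. The endpoints, individual curves and listing are not affected. It is worth correcting because the plan as written produces a misleading table and the correction is nearly free.

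**What to change.** In SAP 14.10 and Appendix B entry 14.3.6.2, delete the post-dose by-time-point summary of analyzer data. Keep the individual curves (Figure 14.3.6.2) and Listing 16.2.5.9, with readings after IV glucose marked, so that text, index and shells agree. In the index, tag 14.3.6.2 as a figure, remove the duplicate number and add Listing 16.2.5.9, which now appears only among the shells. State that group mean response is taken from the fixed-time laboratory samples.

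If a table is kept, define the time windows in advance, print n per window, and footnote that post-dose sampling depends on the glucose value, so the means do not estimate the group mean.

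The cost is a short SAP edit and a flag in one figure and one listing. The checking schedule itself need not change. The loss is that there will be no group-level analyzer means after 30 minutes.

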14.11 Immunogenicity

Occurrence of ADA will be analyzed descriptively. ADA and results from associated characterization assays will be presented descriptively.

ADA will be derived from the number of patients having an ADA-positive sample during the trial.

Positive anti-dasiglucagon antibody samples from treatment-induced or treatment-boosted (titer increase above 4-fold) is defined as ADA-positive.

15. CHANGES TO PROTOCOL-SPECIFIED ANALYSES

No changes were made to the protocol-specified analysis.

17. APPENDICES

APPENDIX A: PRESENTATION OF DATA AND PROGRAMMING SPECIFICATIONS

General

- Specialized text styles, such as bold, italics, borders, shading, and superscripted and subscripted text will not be used in tables, figures, and data listings (TFLs) unless they add significant value to the TFL.
- Only standard keyboard characters are to be used in tables and data listings.
- Special characters, such as nonprintable control characters and printer- or font-specific characters, will not be used in a TFL.
- Hexadecimal character representations are allowed (eg, μ , α , and β).
- All footnotes will be left justified and at the bottom of a page. Footnotes must be used sparingly and add value to the TFL.

Tables

- Means and medians will be presented to 1 decimal place more than the raw data. Standard deviations will be presented to 2 decimal places more than the raw data. Minimums and maximums will be reported with the same number of decimal places as the raw data.
- Percentages will be presented to the tenths place.
- For frequency counts of categorical variables, categories whose counts are zero will be displayed for the sake of completeness. For example, if none of the subjects discontinue due to “lost to follow-up,” this reason will be included in the table with a count of 0. Categories with zero counts will not have zero percentages displayed.
- Lower and upper CI values must be presented to 1 decimal place more than the raw/derived data (ie, to the same number of decimal places as the mean).
- Percentiles (eg, 25% and 75%) must be presented to 1 decimal place more than the raw/derived data.
- For all inferential analyses, P values will be rounded to 4 decimal places (or at the highest level of precision) with a leading zero (0.0001). P values less than 0.0001 will be presented as “<0.0001.”
- The last footnotes will be:
 - “Source: xxx”, where xxx indicates the source table number(s), if applicable (in case aggregated results, such as the mean or median, are plotted), source listing(s) (in case individual responses are plotted), and/or source dataset(s) (eg, ADaM).
 - “PROGRAM SOURCE:...\\xx.sas, DATA CUT-OFF DATE: DD Mmm YYYY, RUN DATE: DD Mmm YYYY hh:mm”.

Figures

- Legends will be used for all figures with more than 1 variable or item displayed.
- Figures will be in black and white but can be in color to add value to the clarity and readability of a figure. Lines must be wide enough to see the line after being copied.
- The last footnotes will be:
 - “Source: xxx”, where xxx indicates the source listing number(s) and/or source dataset(s) (eg, ADaM).
 - “PROGRAM SOURCE:...\\xx.sas, DATA CUT-OFF DATE: DD Mmm YYYY, RUN DATE: DD Mmm YYYY hh:mm”.

Listings

- If not otherwise specified, all data listings will be sorted by center, subject number, visit, and date/time, as appropriate.
- All date values will be presented in a SAS® statistical software, version 9.4 or higher (SAS Institute Inc) date format (eg, 29AUG2001).
- All observed time values will be presented using a 24-hour clock format (HH:MM:SS) (eg, 01:35:45 or 11:26). Seconds will only be reported if they were measured as part of the study.
- The last footnote will be “PROGRAM SOURCE:...\\xx.sas, DATA CUT-OFF DATE: DD Mmm YYYY, RUN DATE: DD Mmm YYYY hh:mm”.

Missing or Incomplete Dates (ie, Adverse Events and Concomitant Medications)

The most conservative approach will be systematically considered. If the adverse event (AE) onset date is missing/incomplete, it is assumed to have occurred during the study treatment phase (ie, considered a treatment-emergent AE) except if the partial onset date or other data, such as the stop date, indicates differently. Similarly, a medication with partial start and stop dates could be considered as both a prior and concomitant medication.

The following algorithms will be applied to missing and incomplete start and stop dates:

Start Dates

- If the day portion of the start date is missing, then the start date will be estimated to be equal to the date of the first dose of study drug, provided the start month and year are the same as the date of the first dose of study drug and stop date is either after the date of the first dose of study drug or completely missing. Otherwise, the missing day portion will be estimated as “01.”
- If both the day and month portions of the start date are missing, then the start date will be estimated to be equal to the date of the first dose of study drug, provided the start year is the same as the date of the first dose of study drug and stop date is either after the date of

the first dose of study drug or completely missing. Otherwise, the event will be assumed to start on the first day of the given year (eg, ??-??-2013 is estimated as 01-JAN-2013).

- If the start date is completely missing and stop date is either after the date of the first dose of study drug or completely missing, then the start date will be estimated to be equal to the date of the first dose of study drug. Otherwise, the start date will be estimated to be the first day of the same year as the stop date. All other non-AE and non-concomitant medication day calculations where only partial dates are available will be handled as follows: the first day of the month will be used in the calculations if the day part of a start date is missing, and January 1 will be used if both the month and day parts of a start date are missing.

Stop Dates

- If only the day of resolution is unknown, the day of resolution of the event will be assumed to be the last day of the month (eg, ??-JAN-2013 will be treated as 31-JAN-2013).
- If both the day and month of resolution are unknown, the day of resolution of the event will be assumed to be the last day of the year (eg, ??-??-2013 will be treated as 31-DEC-2013).
- If the stop date of the event is completely missing or event is continuing, the event resolution will be assumed to be after the first dose of study drug, and the stop date will be imputed using the last known date on the study.

Standard Calculations

Variables requiring calculation will be derived using the following formulas:

- Days: A duration expressed in days between 1 date (date1) and another later date (date2) is calculated using the following formula: duration in days = date2 – date1 + 1
- Months: A duration expressed in months is calculated using the INTCK function of SAS using the following formula: months = intck('month', 'date1'd, date2'd, 'continuous')
- Years: A duration expressed in years between 1 date (date1) and another later date (date2) is calculated using the following formula: duration in years = intck('year', 'date1'd, 'date2'd, 'continuous')
- Body Mass Index (BMI): BMI is calculated using height and weight using and is calculated using the following formula: $BMI \text{ (kg/m}^2\text{)} = \text{weight (kg)} / [\text{height (cm)} / 100]^2$
- Change from baseline: Change from baseline will be calculated using the following formula: change = analysis value (including the baseline value) – baseline value

- Percent change from baseline: Percent change from baseline will be calculated using the following formula: percent change from baseline = (analysis value (including the baseline value) – baseline value)/baseline value × 1

